Clinical Trial Protocol: ADX-102-DED-021

Protocol Title: A Multi-Center, Double-Masked, Randomized, Vehicle-Controlled, Parallel-Group Clinical Trial Evaluating the Safety of 0.25% Reproxalap Ophthalmic Solution in Subjects with Dry Eye Disease

Protocol Number: ADX-102-DED-021

Study Phase: 3

Product Name: 0.25% Reproxalap Ophthalmic Solution
[REDACTED]

[figure not shown]
Indication: Dry Eye Disease (DED)

Investigators: Multi-Center
Aldeyra Therapeutics, Inc.

Sponsor: [name]
[name]

Contract Research Organization:
[REDACTED]

IRB:
[REDACTED]

Confidentiality Statement

This protocol contains confidential, proprietary information of Ora, Inc. and Aldeyra, Inc.
Further dissemination, distribution, or copying of this protocol or its contents is strictly
prohibited.

SPONSOR PERSONNEL

[figure not shown]
ORA PERSONNEL

SYNOPSIS

Protocol Title:	A Multi-Center, Double-Masked, Randomized, Vehicle-Controlled, Parallel-Group Clinical Trial Evaluating the Safety of 0.25% Reproxalap Ophthalmic Solution in Subjects with Dry Eye Disease
Protocol Number:	ADX-102-DED-021
Study Drug:	1) 0.25% Reproxalap Ophthalmic Solution (reproxalap) 2) Vehicle Ophthalmic Solution (vehicle)
Study Phase:	3
Study Objective:	To compare the safety of reproxalap to vehicle in patients with dry eye disease
Overall Study Design	
Structure:	Multi-center, double-masked, randomized trial
Duration:	An individual subject's participation is estimated to be approximately 6 weeks (42 days) or 1 year (360 days).
Control:	Vehicle Ophthalmic Solution (vehicle)
Dosage/Dose Regimen:	Subjects will qualify for enrollment at Visit 1 and will be randomized to one of the following treatments: 
•Treatment A: 0.25% Reproxalap Ophthalmic Solution•Treatment B: Vehicle Ophthalmic Solution Subjects who are in the trial for 6 weeks will dose four times daily (QID) with reproxalap or vehicle for the first 4 weeks and two times daily (BID) for the remaining two weeks. Subjects who are in the trial for 1 year (LTFU) will dose QID with reproxalap or vehicle for the first 4 weeks and BID for the remaining 11 months.
Summary of Visit Schedule:	3 visits over the course of approximately 6 weeks OR 7 visits over the course of 1 year (LTFU Cohort)

	
• Visit 1 = Screening & Randomization• Visit 2 = Day 29 ± 3, 4-Week Follow-Up• Visit 3 = Day 43 ± 4, 6-Week Follow-Up (Exit for approximately 300 subjects)• Visit 4 = Day 90 ± 7, 3-Month follow-up• Visit 5 = Day 180 ± 7, 6-Month follow-up• Visit 6 = Day 270 ± 10, 9-Month follow-up• Visit 7 = Day 360 ± 10, 1-Year follow-up & Exit
Measures Taken to Reduce Bias:	Randomized treatment assignment, double-masked trial
Study Population Characteristics	
Number of Subjects:	Approximately 1050 subjects are expected to be screened to enroll 850 subjects into the trial. Approximately 550 subjects will continue after Week 6 for the Long-Term Follow-up portion, with the goal of approximately at least 100 reproxalap subjects completing at 1 year.
Condition/Disease:	Dry Eye Disease (DED)

Inclusion Criteria:	Subjects must meet all of the following criteria: 
1. At least 18 years of age (either gender and any race);2. Ability to provide written informed consent and sign the Health Information Portability and Accountability Act (HIPAA) form;3. Reported history of dry eye for at least 6 months prior to Visit 1;4. History of use or desire to use eye drops for dry eye symptoms within 6 months of Visit 1; 
Exclusion Criteria:	Subjects must not meet any of the following criteria: 
1. Clinically significant slit lamp findings at Visit 1 that may include active blepharitis, meibomian gland dysfunction (MGD), lid margin inflammation, or active ocular allergies that require therapeutic treatment, and/or in the opinion of the investigator may interfere with study parameters;2. Diagnosis of an ongoing ocular infection (bacterial, viral, or fungal), or active ocular inflammation at Visit 1;3. Contact lens use within 7 days of Visit 1 or anticipate using contact lenses during the trial;4. Eye drop use within 2 hours of Visit 1;

	
5. Previous laser-assisted in situ keratomileusis (LASIK) surgery within the last 12 months; 7. Planned ocular and/or lid surgeries over the study period or any ocular surgery within 6 months of Visit 1;8. Temporary punctal plugs during the study that have not been stable within 30 days of Visit 1;9. Use of and unwillingness to discontinue topical ophthalmic prescription (including medications for glaucoma) or over-the-counter (OTC) solutions, artificial tears, gels or scrubs for the duration of the trial (excluding medications allowed for the conduct of the trial); 
	
11. Pregnancy, nursing, or planned pregnancy during the conduct of the trial;12. Unwillingness to submit a urine pregnancy test at Visit 1 and Visit 43 (6-week subjects)/Visit 7 (LTFU subjects) (or early termination visit) if of childbearing potential. (Non-childbearing potential is defined as a woman who is permanently sterilized [e.g., has had a hysterectomy or tubal ligation], or is post-menopausal [without menses for 12 consecutive months];13. If of childbearing potential, unwillingness to use an acceptable means of birth control.

	
(Acceptable methods of contraception include: hormonal – oral, implantable, injectable, or transdermal contraceptives; mechanical – spermicide in conjunction with a barrier such as a diaphragm or condom; intrauterine device [IUD]; or surgical sterilization of partner. For non-sexually active males or females, abstinence may be regarded as an adequate method of birth control; however, if the subject becomes sexually active during the study, he/she must agree to use adequate birth control as defined above for the remainder of the trial.);
 
14. Known allergy and/or sensitivity to the test article or its components;
 
15. A condition or be in a situation which the investigator interprets may put the subject at significant risk, may confound the study results, or may interfere significantly with the subject's participation in the study;
 
16. Abnormal endothelial cell count (LTFU subjects only);
 
17. Current enrollment in an investigational drug or device study or have used an investigational drug or device within 30 days of Visit 1;
 
18. Previous reproxalap use within the past year;
 
19. Inability or unwillingness to follow instructions, including participation in all study assessments and visits.

Study Formulations and Formulation Numbers:	0.25% Reproxalap Ophthalmic Solution Vehicle Ophthalmic Solution
Evaluation Criteria	
Primary Safety Endpoints	
Proportion of subjects that experience at least one treatment-emergent severe adverse event (TE-SAE) of a visual

	
acuity decrease (defined as an increase of 0.22 or greater in logMAR score) categorized as probably or definitely related to Investigational Product (IP)
 
• Proportion of subjects that experience at least one TE-SAE of an IOP increase from baseline of ≥ 10 mm Hg AND report an IOP of > 25 mm Hg categorized as probably or definitely related to IP• Proportion of subjects that experience at least one TE-SAE of the cornea detected via slit-lamp biomicroscopy categorized as probably or definitely related to IP• Proportion of subjects that experience at least one TE-SAE of the retina detected via fundoscopy categorized as probably or definitely related to IP
Safety Evaluation Criteria:	
• Visual acuity• Slit-lamp evaluation• Adverse event query• Intraocular Pressure (IOP)• Dilated fundoscopy• Central Cornea Endothelial Cell Counts (1-year LTFU subjects)• Blood chemistry and hematology analysis in a subset of subjects (1-year LTFU subjects only)• Unanesthetized Schirmer's Test 

Other Measures:	
• Urine Pregnancy Test
General Statistical Methods and Types of Analyses	
Analysis Populations	

• Safety Population – The Safety population will include all subjects receiving treatment from whom at least one safety measurement is obtained following the first dose of study drug. The Safety population will be analyzed for all safety assessments. Subjects in the Safety population will be analyzed as treated.	

- **Safety-LTFU Population** – The Safety population will include all LTFU subjects receiving treatment from whom at least one safety measurement is obtained following the first dose of study drug. The Safety-LTFU population will be analyzed for all safety assessments. Subjects in the Safety-LTFU population will be analyzed as treated.

Sample Size

[figure not shown]
[figure not shown]
[figure not shown]
[figure not shown]

Table 1: Assumed True Event Proportions

[figure not shown]
[figure not shown]

[figure not shown]
Table 2: Assumed True Event Proportions

Multiplicity

All primary safety endpoints will be tested with an overall study-wide two-sided alpha level of 0.05 with the primary safety endpoints evaluated using the Safety population with 6 weeks of follow-up being tested at a two-sided alpha level of 0.0165 and the primary safety endpoints using the Safety-LTFU population with 6 months (and 1-year) of follow-up being tested at a two-sided alpha level of 0.0335.

For the primary safety endpoints using the Safety population with 6 weeks of follow-up, Bonferroni correction will be used to account for multiple endpoint testing. For example, each primary safety endpoint tested using the Safety population with 6 weeks of follow-up will be assessed at the two-sided alpha level of 0.004125. For the interim analyses, no type I error adjustment will be made as 100% of the information will be available for the primary endpoints using the Safety population with 6-weeks of follow-up.

Primary Safety Analyses

The following endpoints will be formally tested in both the Safety and Safety-LTFU populations at interim and final analysis [REDACTED]

- Proportion of subjects that experience at least one TE-SAE of a visual acuity decrease (defined as an increase of 0.22 or greater in logMAR score) categorized as probably or definitely related to IP
- Proportion of subjects that experience at least one TE-SAE of an IOP increase from baseline of ≥ 10 mm Hg AND report an IOP of > 25 mm Hg categorized as probably or definitely related to IP
- Proportion of subjects that experience at least one TE-SAE of the cornea detected via slit-lamp biomicroscopy categorized as probably or definitely related to IP
- Proportion of subjects that experience at least one TE-SAE of the retina detected via fundoscopy categorized as probably or definitely related to IP

The primary safety comparisons in this trial will be between 0.25% Reproxalap versus Vehicle in the Safety Population using the following primary estimand:

Estimand 1

- Populations:
 - Subjects with DED defined through enrollment criteria that are enrolled in either the 6-week follow-up or 1-year follow-up schedule.
 - Subjects with DED defined through enrollment criteria that are enrolled in the 1-year follow-up schedule only.
- Endpoints:

Safety population at 6 weeks:

Proportion of subjects that experience at least one TE-SAE of a visual acuity decrease (defined as an increase of 0.22 or greater in logMAR score) categorized as probably or definitely related to IP within 6 weeks of study drug dosing in the Safety

populationProportion of subjects that experience at least one TE-SAE of an IOP increase from baseline of ≥ 10 mm Hg AND report an IOP of > 25 mm Hg categorized as probably or definitely related to IP within 6 weeks of study drug dosing in the Safety population

- Proportion of subjects that experience at least one TE-SAE of the cornea detected via slit-lamp biomicroscopy categorized as probably or definitely related to IP within 6 weeks of study drug dosing in the Safety population
- Proportion of subjects that experience at least one TE-SAE of the retina detected via fundoscopy categorized as probably or definitely related to IP within 6 weeks of study drug dosing in the Safety population

Safety-LTFU population within 6 months (or 1 year):

- Proportion of subjects that experience at least one TE-SAE of a visual acuity decrease (defined as an increase of 0.22 or greater in logMAR score) categorized as probably or definitely related to IP within 6 months/1 year of study drug dosing in the Safety-LTFU population
Proportion of subjects that experience at least one TE-SAE of an IOP increase from baseline of ≥ 10 mm Hg AND report an IOP of > 25 mm Hg categorized as probably or definitely related to IP within 6 months/1 year of study drug dosing in the Safety-LTFU population
- Proportion of subjects that experience at least one TE-SAE of the cornea detected via slit-lamp biomicroscopy categorized as probably or definitely related to IP within 6 months/1 year of study drug dosing in the Safety-LTFU population
- Proportion of subjects that experience at least one TE-SAE of the retina detected via fundoscopy categorized as probably or definitely related to IP within 6 months/1 year of study drug dosing in the Safety-LTFU population
- Intercurrent event:
 - Discontinuation of study medications is ignored, measures obtained after discontinuation of study medication will be analyzed. [treatment policy strategy]
 - Non-optimal compliance is ignored, measures will be analyzed regardless of treatment compliance. [treatment policy strategy]
 - Use of prohibited alternative therapies is ignored, measures obtained after initiation of prohibited therapies will be analyzed. [treatment policy strategy]
 - Discontinuation of study, subjects that discontinue study prior to time point of interest for an endpoint (Ex. 6 weeks or 6

- months/1 year) AND do not experience event of interest will not be analyzed. [principal stratum strategy]
- Discontinuation of study, values post-discontinuation will not be imputed. [while on treatment strategy]
- Population-level summaries:
 - Difference in the proportion of subjects that experience at least one TE-SAE of a visual acuity decrease (defined as an increase of 0.22 or greater in logMAR score) categorized as probably or definitely related to IP
 - Difference in the proportion of subjects that experience at least one TE-SAE of an IOP increase from baseline of ≥ 10 mm Hg AND report an IOP of > 25 mm Hg categorized as probably or definitely related to IP
 - Difference in the proportion of subjects that experience at least one TE-SAE of the cornea detected via slit-lamp biomicroscopy categorized as probably or definitely related to IP
 - Difference in the proportion of subjects with at least one TE-SAE of the retina detected via fundoscopy categorized as probably or definitely related to IP

Frequencies and percentages of subjects from each treatment group will be reported. Differences in proportions for each endpoint will also be reported.

Sensitivity analyses of the primary safety endpoints may include repeating primary analyses with alternative handling of intercurrent events with different estimands. In addition, sensitivity analyses using incidence rates (events/person-time) will be produced. Details will be outlined in the Statistical Analysis Plan (SAP), which will dominate any statistical language herein.

Other Safety Analyses

Frequencies and percentages of subjects with treatment-emergent adverse events (TEAEs), serious TEAEs, and TEAEs causing premature treatment discontinuation will be provided by treatment group. An AE is treatment emergent if it occurs or worsens after the first dose of study treatment. Furthermore, frequencies will be given of subjects with TEAEs by system organ class and preferred term for the following categories of AEs:

- All TEAEs
- TEAEs at least possibly related to study treatment
- TEAEs leading to study treatment discontinuation
- Serious TEAEs (SAEs)

- By maximal severity
- By study day of onset

Separate analyses will be performed for ocular and non-ocular AEs. Further analyses of AEs will be specified in the SAP.

Other safety endpoints will be summarized by treatment group and visit using descriptive statistics using the Safety population or Safety-I.TFU population. Changes or shifts from baseline will also be summarized where appropriate. Assessments performed by eye will be summarized separately for right eye (OD) and left eye (OS).

For quantitative safety endpoints, comparisons between treatment groups will be made at the eye level. [REDACTED]

[REDACTED]

Summary of Known and Potential Risks and Benefits to Human Subjects

There are no known safety risks of topical ocular reproxalap, which has been administered to 968 subjects across 8 Phase 2 and Phase 3 clinical trials in concentrations of 0.1%, 0.25%, and 0.5%, up to 4-times-daily for 12 weeks and 8-times-daily tapered to 4-times-daily over 4 weeks in healthy volunteers and in subjects with dry eye disease, allergic conjunctivitis, and noninfectious anterior uveitis. No consistent changes in visual acuity, slit-lamp evaluation, IOP, dilated fundoscopy, or non-ocular adverse events have been observed. No treatment-related serious adverse events have been observed. [REDACTED]

[REDACTED]

Reproxalap has demonstrated consistent, statistically significant, and clinically meaningful activity in dry eye disease, allergic conjunctivitis, and noninfectious anterior uveitis as assessed by change from baseline and improvement over vehicle.

TABLE OF CONTENTS

SYNOPSIS	4
TABLE OF CONTENTS	16
LIST OF ABBREVIATIONS	20
1 INTRODUCTION	21
2 STUDY OBJECTIVES	22
3 CLINICAL HYPOTHESES	22
4 OVERALL STUDY DESIGN	22
5 STUDY POPULATION	24
5.1 Number of Subjects (approximate)	24
5.2 Study Population Characteristics	24
5.3 Inclusion Criteria	25
5.4 Exclusion Criteria	25
5.5 Withdrawal Criteria (if applicable)	26
6 STUDY PARAMETERS	27
6.1 Efficacy Measures	27
6.2 Safety Measures	27
6.3 Other Measures	27
7 STUDY MATERIALS	28
7.1 Study Drug(s)	28
7.1.1 Study Drug(s)/ Formulation(s)	28
7.1.2 Study Drug Packaging Configuration	28
7.1.3 Study Drug Storage and Accountability	28
7.1.4 Instructions for Dispensation, Use, and Administration	28
7.2 Other Study Supplies	29
8 STUDY METHODS AND PROCEDURES	29
8.1 Subject Entry Procedures	29
8.1.1 Overview	29
8.1.2 Informed Consent	29
8.1.3 Washout Intervals	29
8.1.4 Procedures for Final Study Entry	29
8.1.5 Methods for Assignment to Treatment Groups:	29
8.2 Concurrent Therapies	30

8.2.1	Prohibited Medications/Treatments	30
8.2.2	Escape Medications	30
8.2.3	Special Diet or Activities	30

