H_{A4} : The proportion of subjects that experience at least one TE-SAE of the retina detected via fundoscopy categorized as probably or definitely related to IP is greater in the 0.25% Reproxalap group than the Vehicle group in the Safety population within 6 weeks of study drug treatment.

Long-Term Follow-up Subjects at (6 Months or 1 Year)

H_{05} : There is no difference in the proportion of subjects that experience at least one TE-SAE of a visual acuity decrease (defined as an increase of 0.22 or greater in logMAR score) categorized as probably or definitely related to IP in the 0.25% Reproxalap group vs. Vehicle group in the Safety-LTFU population within 6 months of study drug treatment (or 1 year).

H_{A5} : The proportion of subjects that experience at least one TE-SAE of a visual acuity decrease (defined as an increase of 0.22 or greater in logMAR score) categorized as probably or definitely related to IP is greater in the

0.25% Reproxalap group than the Vehicle group in the Safety-LTFU population within 6 months of study drug treatment (or 1 year).

H_{06} : There is no difference in the proportion of subjects that experience at least one TE-SAE of an IOP increase from baseline of ≥ 10 mm Hg AND report an IOP of > 25 mm Hg categorized as probably or definitely related to IP in the 0.25% Reproxalap group vs. Vehicle group in the Safety-LTFU population within 6 months of study drug treatment (or 1 year).

H_{A6} : The proportion of subjects that experience at least one TE-SAE of an IOP increase from baseline of ≥ 10 mm Hg AND report an IOP of > 25 mm Hg categorized as probably or definitely related to IP is greater in the 0.25% Reproxalap group than the Vehicle group in the Safety-LTFU population within 6 months of study drug treatment (or 1 year).

H_{07} : There is no difference in the proportion of subjects that experience at least one TE-SAE of the cornea detected via slit-lamp biomicroscopy categorized as probably or definitely related to IP in the 0.25% Reproxalap group vs. Vehicle group in the Safety-LTFU population within 6 months of study drug treatment (or 1 year).

H_{A7} : The proportion of subjects that experience at least one TE-SAE of the cornea detected via slit-lamp biomicroscopy categorized as probably or definitely related to IP is greater in the 0.25% Reproxalap group than the Vehicle group in Safety-LTFU population within 6 months of study drug treatment (or 1 year).

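### Is the 0.0335 for the long-term follow-up tests spent twice, at 6 months and again at 1 year, because the interim analyses carry no type I error adjustment?

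*Combined protocol and SAP*

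**What the plan says.** The Multiplicity paragraphs of the synopsis set a study-wide two-sided level of 0.05 for all primary safety endpoints. The 6-week Safety family gets 0.0165, and Bonferroni over its four endpoints gives 0.004125 each. The Safety-LTFU endpoints are described as "with 6 months (and 1-year) of follow-up being tested at a two-sided alpha level of 0.0335". No per-endpoint level for them is readable.

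The 6-week paragraph ends with the interim rule, "no type I error adjustment will be made as 100% of the information will be available for the primary endpoints using the Safety population" with 6 weeks of follow-up. The next part of the synopsis, Primary Safety Analyses, says the endpoints "will be formally tested in both the Safety and Safety-LTFU populations at interim and final analysis"; that sentence then runs into a redaction.

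Elsewhere the two LTFU time points are joined by a different word. Estimand 1 has "Safety-LTFU population within 6 months (or 1 year" and the LTFU alternatives in Section 10.2 have "greater in the 0.25% Reproxalap group than the Vehicle group in the Safety-LTFU population within 6 months of study drug treatment (or 1 year", each closing the bracket there.

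Sections 10.4.4 (Multiplicity Adjustments) and 10.4.8 (Interim Analyses) and the opening of 10.4.5 are blacked out. The synopsis also says that the SAP overrides the protocol's statistical language.

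**The concern.** Two things look wrong. First, the reason for making no interim adjustment is that the 6-week data will be complete. Complete 6-week data say nothing about how much LTFU information is in hand, yet the LTFU endpoints are also tested at interim and final. Read literally, the waiver covers tests that its reason does not.

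Second, one figure of 0.0335 is attached to two time points, with no readable statement of whether it is used once, shared, or used at each. The change between *and* and *or* adds to the doubt about which LTFU result is the formal one.

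The error at stake is a false safety signal. The alternatives in Section 10.2 all state that the proportion is greater on reproxalap, so an inflated level would mean wrongly declaring harm. If the two time points disagreed, the choice between them could also look post hoc.

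**Working it through.** **Inputs from the synopsis.** Overall 0.05; 6-week family 0.0165; LTFU family 0.0335; four endpoints per family. Safety 850 and LTFU 550 subjects at 2:1, so about 567 vs 283 and 367 vs 183.

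**The plan's own figures reproduce.** 0.0165 + 0.0335 = 0.05, and 0.0165/4 = 0.004125.

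**Reading A: 0.0335 is the total.** Bonferroni over four endpoints and two time points gives 0.0335/8 = 0.0041875 per test, and 8 × 0.0041875 + 0.0165 = 0.05. If only one time point is formal, each LTFU endpoint gets 0.0335/4 = 0.008375. With all tests independent, overall error is 1 − (1 − 0.008375)^4 × (1 − 0.004125)^4 = 0.0489. The cap holds either way.

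**Reading B: 0.008375 is used in full at both time points.** This per-endpoint level is borrowed from the 6-week rule. Let x be the chance that an endpoint rejects at either look (bivariate normal). Overall error is 1 − (1 − x)^4 × (1 − 0.004125)^4.

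| Correlation between looks (assumed) | x, two-sided | Overall, two-sided | Overall, reproxalap worse only |
|---|---|---|---|
| 0 | 0.01668 | 0.080 | 0.041 |
| 0.71 | 0.01486 | 0.074 | 0.037 |
| 0.95 | 0.01141 | 0.061 | 0.031 |

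The comparators are 0.05 two-sided and 0.025 in one direction. In large samples, reading B breaks the cap.

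**Reading B with rare events.** The planned test and assumed rates are redacted, so the following are assumptions: two-sided Fisher tests, four independent endpoints, equal true rates in both arms, half of the 1-year events by 6 months and 6/52 of them by 6 weeks, and no dropout. One million simulated trials per rate gave:

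| 1-year event rate | LTFU family, two-sided | Overall, two-sided | Overall, reproxalap worse only |
|---|---|---|---|
| 1% | 0.011 | 0.011 | 0.0001 |
| 2% | 0.027 | 0.028 | 0.004 |
| 3% | 0.036 | 0.037 | 0.009 |
| 5% | 0.041 | 0.046 | 0.016 |
| 10% | 0.045 | 0.052 | 0.021 |

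Overall two-sided error stays under 0.05 up to a rate of 5% and passes it marginally at 10%. In the direction of the alternatives it stays under 0.025 throughout. The LTFU family alone passes its two-sided 0.0335 from 3% upward; the unused part of the 6-week share absorbs this up to 5%.

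**With heavy dropout.** The synopsis plans LTFU "with the goal of approximately at least 100 reproxalap subjects completing at 1 year", and leavers before the time point who "AND do not experience event of interest will not be analyzed" drop out of the denominator. Take 100 of 367 completing 1 year, 233 of 367 completing 6 months (assumed), the same fractions on vehicle, and leavers at half the risk of the interval in which they leave. The two-sided LTFU family error is then 0.005, 0.016, 0.024 and 0.033 at 1%, 2%, 3% and 5% (60,000 trials per rate), against 0.0335.

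**What a tighter split would cost.** With no events among 183 on vehicle, Fisher p is 0.0063 for 13 of 367 on reproxalap, 0.0068 for 14 and 0.0036 for 15. Moving from 0.008375 to 0.0041875 per test raises the number needed from 13 to 15.

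**The case for a change.** The best case for a change rests on readable text alone. The waiver opens without restriction, its reason is confined to "available for the primary endpoints using the Safety population with 6-weeks of follow-up", and the next paragraph puts the LTFU endpoints into the same interim and final analyses. That mismatch does not depend on what is blacked out. These are the primary endpoints, and a few sentences would settle the matter.

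The mismatch stands as a drafting fault, but it does not show that error is uncontrolled. The waiver closes a paragraph whose other sentences concern only the 6-week Safety endpoints, and its reason names the same population, so it can be read as limited to them. Reading B contradicts the opening sentence of the Multiplicity text, which holds all primary endpoints to 0.05 and has already spent that amount exactly. The *and*/*or* difference also fits one set of endpoints evaluated at whichever follow-up an analysis covers; Section 10.4.6 plans its LTFU summaries for 6 months or 1 year in just that way.

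An allocation may sit in the redacted sections, in the cut-off end of the interim-and-final sentence, or in the SAP. Its absence from the readable text is not evidence that it is absent from the plan.

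**Conclusion.** No change to the plan is called for. The stated 0.05 cap and the single 0.0335 point to a total over the LTFU tests. An analyst would treat it so and take the split from the SAP or from Sections 10.4.4 and 10.4.8. What is left is clerical: an interim sentence worded more widely than its reason, and *and* in one place where *or* stands in others.

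The figures of 0.074 two-sided and 0.037 directional are large-sample values for a reading that the cap does not support, so they are not a consequence of the plan. Under that same reading, Fisher tests without dropout keep overall two-sided error at 0.011 to 0.046 for 1-year rates of 1% to 5%, and at 0.052 for 10%. Those results assume the test, the event timing and independent endpoints. They would not excuse full use at both time points if events were common. A tighter split would also make a real harm signal slightly harder to detect, for no demonstrated gain.

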4 OVERALL STUDY DESIGN

The ADX-102-DED-021 clinical trial is a Phase 3, multicenter, randomized, double-masked, parallel-group, vehicle-controlled design. Subjects will be randomized to one of the following treatment groups at Visit 2:

[figure not shown]
- 0.25% Reproxalap Ophthalmic Solution (reproxalap)
- Vehicle Ophthalmic Solution (vehicle)

[figure not shown]
Approximately 850 subjects will be randomly assigned to one of the two treatment groups (2:1) to receive either reproxalap or vehicle as topical ophthalmic drops administered bilaterally QID for four weeks followed by BID dosing for weeks 5-6. Approximately 550 subjects will dose QID for four weeks and continue dosing BID for the following 11 months. Subjects, Sponsor, CRO, and site personnel will be masked to treatment assignment.

All subjects will dose with randomized treatment QID between Visit 1 and Visit 2 and switch to BID dosing between Visit 2 and Visit 4 or between Visits 2 and Visit 7 for the long-term follow-up group.

The total number of expected participants, including screen failures, is approximately 1050 subjects.

A study flow chart appears below:

Subjects who terminate early during the treatment period will be asked to complete safety assessments prior to commencement of alternative DED therapy (if possible). [REDACTED]

[REDACTED]

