5 STUDY POPULATION

5.1 Number of Subjects (approximate)

It is estimated that approximately 1050 subjects will be screened to enroll approximately 850 subjects in a 2:1 ratio of reproxalap to vehicle. Approximately 550 subjects will continue after Week 6 for long-term follow-up, with the goal of at least 100 reproxalap subjects completing the long-term follow-up.

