6.2 Other Safety Endpoints

- Visual acuity
- Slit-lamp evaluation
- Adverse event query
- Intraocular Pressure (IOP)
- Dilated fundoscopy
- Central Cornea Endothelial Cell Counts (1-year LTFU subjects only)
- Blood chemistry and hematology analysis in a subset of subjects (1-year LTFU subjects only)
- Unanesthetized Schirmer's Test

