10.4.2 Unit of Analysis

Safety endpoints will be analyzed for both eyes. For subject-level efficacy endpoints, the unit of analysis will be the subject. For endpoints assessed on each eye individually, the unit of analysis will be right eye (OD) or left eye (OS).

[figure not shown]

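### By-eye quantitative safety endpoints: the readable right-eye-or-left-eye unit points to two one-eye comparisons, where one comparison using both eyes would be more precise

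*Combined protocol and SAP*

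**What the plan says.** Section 4 randomises subjects, not eyes: "Approximately 850 subjects will be randomly assigned to one of the two treatment groups (2:1"). Both eyes then get the assigned product, as "topical ophthalmic drops administered bilaterally QID for four weeks" and at a lower frequency afterwards.

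Three readable statements set the level of analysis for measurements taken on each eye:

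- Synopsis, Other Safety Analyses: "For quantitative safety endpoints, comparisons between treatment groups will be made at the eye level". The text directly after this sentence is redacted.
- Section 10.4.2: "Safety endpoints will be analyzed for both eyes", and then "For endpoints assessed on each eye individually, the unit of analysis will be right eye (OD) or left eye (OS").
- Synopsis, Other Safety Analyses: "Assessments performed by eye will be summarized separately for right eye (OD) and left eye (OS"). Section 10.4.6 repeats this for the main text.

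The Synopsis sentence names no endpoints. Section 6.2 lists the other safety endpoints. The ones that are quantitative and measured by eye appear to be visual acuity, intraocular pressure, Schirmer's test and, for the long-term cohort, "Central Cornea Endothelial Cell Counts (1-year LTFU subjects only"). Blood chemistry and haematology are quantitative too, but have no eye level.

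The four primary safety endpoints are proportions of subjects, and the readable alpha allocation covers only those.

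**The concern.** The subject is what was randomised, and the treatment contrast is the same for both eyes. There is therefore one question per endpoint and visit: does reproxalap shift the measurement relative to vehicle? If the right eye and the left eye are each taken as the unit, that question gets two answers. Each answer comes from one eye per subject and leaves out what the fellow eye adds. The readable text gives no rule for reading a result seen in one eye and not in the other.

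The trial's objective is safety (Section 2). The primary endpoints count severe events judged probably or definitely related to the product, so they are not sensitive to a modest mean change in pressure, acuity, endothelial count or tear secretion. In the readable text, the quantitative comparisons are the only between-arm look at such a change. In a safety comparison, lost precision makes a real shift easier to miss, and two unranked answers leave room for selective emphasis.

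**Working it through.** The readable plan gives no sample size, power, SD or between-eye correlation for these comparisons, so there is no figure of its own to reproduce.

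**Inputs from the documents.** About 850 subjects at 2:1 (Section 4), roughly 567 and 283. For the long-term cohort, "Approximately 550 subjects will continue after Week 6 for long-term follow-up" (Section 5.1), roughly 367 and 183 if the ratio holds.

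**Assumptions.** Between-eye correlation ρ of 0.5, 0.7 and 0.9 for whichever quantity is analysed; equal variance and equal true effect in the two eyes; both eyes observed; two-sided 0.05; 80% power for a one-eye test.

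**Validity of each one-eye test.** Every subject counts once in a right-eye test and once in a left-eye test, so each should hold its level. A simulation with no true effect (5,000 trials per setting, at 567 v 283 and 367 v 183) gave error rates of 0.046 to 0.056. The two-eye mean gave 0.045 to 0.054.

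**Precision.** With one-eye variance σ², the two-eye mean has variance σ²(1+ρ)/2.

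- Information lost by using one eye: 1 − (1+ρ)/2 = (1−ρ)/2.
- Equivalent gain in subjects from using both: 2/(1+ρ) − 1.
- Detectable difference, one eye, 850 subjects: (1.960 + 0.842) × √(1/283.3 + 1/566.7) = 2.802 × 0.0728 = 0.204 SD.
- The same for 550: 2.802 × √(1/183.3 + 1/366.7) = 2.802 × 0.0905 = 0.253 SD.
- Using both eyes, multiply by √((1+ρ)/2). Power becomes Φ(2.802/√((1+ρ)/2) − 1.960).

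| ρ (assumed) | (1+ρ)/2 | Information lost by one eye | Gain in subjects | Power, both eyes | Detectable, 850 | Detectable, 550 |
|---|---|---|---|---|---|---|
| 0.5 | 0.75 | 25% | 33% | 89.9% | 0.177 SD | 0.219 SD |
| 0.7 | 0.85 | 15% | 18% | 86.0% | 0.188 SD | 0.234 SD |
| 0.9 | 0.95 | 5% | 5% | 82.0% | 0.199 SD | 0.247 SD |

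The reduction factor √((1+ρ)/2) does not depend on the number of subjects. It therefore applies equally at later visits, where fewer remain.

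**Disagreement between eyes.** Treat the two test statistics as bivariate normal with correlation ρ. When each eye has 80% power, exactly one reaches significance 22.6%, 17.4% or 10.0% of the time at ρ = 0.5, 0.7 or 0.9. With no true effect, at least one eye reaches p<0.05 in 9.1%, 8.3% or 7.0% of trials. The simulations gave 0.067 to 0.097 across settings. This second figure matters only if a result in either eye is read as a signal, and the plan states no such rule.

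**The case against.** The strongest reply is that the method is withheld. The text after the Synopsis sentence is redacted, an undisplayed figure follows Section 10.4.2, and the Synopsis says that the SAP prevails over the protocol's statistical language. No SAP text on these comparisons is readable. A comparison at the eye level is also compatible with a model that takes the eye as the observation and includes a subject effect, which is one form of the fix proposed here. This stands: it cannot be said that the plan fails to combine the eyes. The readable rule in 10.4.2 still names one eye or the other as the unit, and should at least match whatever the withheld text says.

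Two stronger readings are tempting, and the documents do not support them.

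- A reader might infer that both eyes are pooled as if they were independent subjects. That would give a nominal 5% test a true error of 2(1 − Φ(1.96/√(1+ρ))), or 11.0% to 15.5% at ρ = 0.5 to 0.9. No readable text describes such pooling, and the right-or-left wording points away from it.
- A reader might infer that half the data are thrown away. Section 10.4.2 says that both eyes are analysed, and the loss per comparison reaches 50% only at ρ = 0.

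It is also fair to say that these are not primary endpoints, that no readable decision rule hangs on them, that Section 10.4.6 readably specifies only descriptive by-eye summaries, and that separate results can reveal a one-eyed effect. These points limit the importance of the issue. They do not make two one-eye comparisons the better choice.

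**Conclusion.** The point holds as a low-cost improvement in method. On the natural reading of 10.4.2 with the Synopsis, each by-eye quantitative safety endpoint gets separate right-eye and left-eye comparisons at each visit. Each keeps its nominal error, but is less precise than one comparison using both eyes of the randomised subject, and the two may disagree.

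The size is modest and rests on an assumed correlation. At 0.5 to 0.9, a one-eye comparison loses 25% to 5% of the information, and the detectable difference is larger by 0.027 to 0.005 SD at 850 subjects (0.204 against 0.177-0.199). A lower correlation would make the gain larger, and a correlation of 1 would remove it. The list of affected endpoints is inferred from Section 6.2. The subject-level primary endpoints and their alpha are not touched.

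**What to change.** In Section 10.4.2 and the Synopsis (Other Safety Analyses), and in the SAP:

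- State one between-arm comparison per by-eye quantitative safety endpoint and visit, with the subject as the independent unit. Use both eyes in one model with a subject random effect or subject-clustered standard errors, or analyse the mean of the two eyes.
- Report a single difference with its 95% CI.
- Name the endpoints covered.
- Keep the separate right-eye and left-eye tables, labelled as descriptive.

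If the withheld text already specifies a joint analysis, only the unit wording in 10.4.2 needs to be aligned with it.

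The cost is a wording change and one standard model per endpoint, with no new data, visits or subjects. The downside is that an effect confined to one eye would show only in the descriptive tables.
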